The proposed prospective investigation will be designed as a non-inferiority study. Study sites will identify and recruit children and/or adults with known CD that are undergoing routine clinical MRE examinations for staging / restaging of intestinal inflammation, follow-up of luminal narrowing / stricturing disease, or follow-up of patients with known internal penetrating disease. Enrolled participants will 1) undergo a dedicated research abbreviated MRE examination within ± 10 days of their clinical MRE, at the convenience of the participant, and 2) participants will be surveyed about their preference / patient experience for the standard-of-care vs. abbreviated MRE protocol. Furthermore, we will ask a series of “trade-off” questions to understand patients’ willingness to tolerate a loss of examination performance to improve patient experience. These tradeoff questions will use a survey method called a discrete choice experiment (DCE), which is a technique based on behavioral economic theory that asks respondents to make a series of discrete choices between medical care strategies.

The parents/guardians of pediatric participants (10-17 years of age) also will receive a similar survey to understand their perspective, and how it may differ from their children.

Board-certified, fellowship-trained radiologists will review both the standard-of-care and abbreviated MRE examinations in separate sessions to document the presence and severity of small bowel inflammation; the presence and features of stricturing disease (and penetrating disease, if present) also will be recorded. The diagnostic performance of the abbreviated MRE protocol will be determined for individual readers and all readers combined, using the standard-of-care protocol as reference standard.

At the end of the proposed study, we will have shown if a patient-centric, noncontrast, abbreviated MRE protocol can be used to evaluate children and adults with CD as well as if such a protocol offers an improved patient experience. If successful, such an abbreviated protocol could enable more frequent patient follow-up imaging, with more individualized patient management and improved patient outcomes, including more frequent transmural healing. Such an abbreviated protocol also could be used in the research setting to assess the effectiveness of candidate anti-inflammatory and anti-stricture (i.e., anti-fibrotic) therapies.

5. DURATION:

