For the dedicated research imaging visit, enrolled participants will undergo dedicated research, abbreviated MRE examination within ± 10 days of their clinical MRE, at the convenience of the participant. Research MRE examinations will be standardized across sites, while clinical MRE examinations will be performed at each site using standard-of-care protocols. Clinical MRI examinations will be performed on both 1.5-T and 3-T MRI scanners from all major scanner manufacturers (i.e., GE HealthCare, Philips Healthcare, and Siemens Healthineers).

Research MRE examinations will be performed on dedicated research MRI scanners which will facilitate participant scheduling. 3-T scanners will be used at Mayo Clinic (Philips Healthcare) and NYU Langone Health (Siemens Healthineers). 1.5-T and 3-T scanners will be used at CCHMC (Philips Healthcare). We plan for these examinations to be performed in less than 15 minutes of scan time, on average.

For research MRE examinations, patients will ingest a standardized volume (weight-based, approximately 20 ml/kg, maximum of 1500ml) of water during the 45-minute period prior to their scheduled imaging time. At $\sim 10\%$ participant recruitment, research MRE examinations will be reviewed to ensure that water is providing adequate bowel distention and image quality.

During and after each research MRE examination, the research coordinator conducting the study visit will document any patient discomfort / distress such as, nausea, vomiting, etc.

Pertinent participant characteristics, including demographics, relevant clinical and laboratory data, and most recent MRI or CT comparison imaging (both reports and DICOM images) will also be obtained at the time of the research visit.

Fellowship-trained, board-certified radiologists from multiple institutions will independently review both the clinical standard-of-care and research abbreviated MRE examinations in separate sessions using a cloud-based image viewer to document the presence and severity of intestinal inflammation. Prior clinical MRE or CT examinations may be made available for comparison. The diagnostic performance of our abbreviated MRE protocol will be determined for individual readers and all readers combined, using standard-of-care clinical MRE examinations as reference standard.

Patient Preference Survey

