The diagnostic performance of our abbreviated MRE protocol will be determined for individual readers and all readers combined, using standard-of-care clinical MRE examinations as reference standard. The presence of clinically meaningful (i.e., moderate-severe) active intestinal inflammation will serve as our primary outcome of interest. These analyses will be performed at the overall examination and individual bowel segment level. Sensitivity, specificity, accuracy, positive predictive value, and negative predictive value will be calculated, with 95% confidence intervals. In addition, the global and individual bowel segment sMaRIA scores will be compared and correlated between clinical and research examinations using Mann-Whitney U tests and Spearman rank-order correlation. The diagnostic performance of the abbreviated MRE protocol for detecting luminal narrowing, stricture disease, internal penetrating disease, and perianal disease will also be calculated, again using clinical MRE examinations as the reference standard. Finally, Fleiss' kappa statistics will be used to evaluate inter-reader agreement for the different imaging features documented. The above results may be compared between readers without and with access to prior MRE or CT imaging when interpreting both the research and clinical MRE examinations.

Survey Analysis:

The analysis will be conducted in STATA, a statistical program. The unit of analysis for all analyses will be the individual participant. We will obtain data on respondent demographics and health characteristics, from baseline questions in the survey. We will summarize continuous outcome measures using means and standard deviations. We will compare continuous outcome measures

across groups (e.g. low versus middle versus high income levels, parent education level, proportion using a CGM) and test for statistical differences between groups using t-tests. We will summarize categorical outcome measures using frequencies and proportions and test for statistical differences between groups using chi-square tests. All statistical analyses will be conducted in Sawtooth Software and Stata (version 17).

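### The only inter-reader statistic named, unweighted Fleiss' kappa, ignores the ordering of the inflammation severity grades

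*Protocol*

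**What the plan says.** Protocol section 9 (Data Analysis/Methods) states near the end of its imaging paragraph that Fleiss' "kappa statistics will be used to evaluate inter-reader agreement for the different imaging features documented". It mentions no weighting, no intraclass correlation and no distinction by type of scale.

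What the readers record is set out in two places. Section 4 (Study Design) has them review both examinations "in separate sessions to document the presence and severity of small bowel inflammation". Section 8 (Study Procedures) repeats the task: "to document the presence and severity of intestinal inflammation". The number of severity grades and the number of readers are not given.

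Two other statements in section 9 bear on the point. The primary outcome is binary: "The presence of clinically meaningful (i.e., moderate-severe) active intestinal inflammation will serve as our primary outcome of interest". The sMaRIA scores have their own sentence, which says that "the global and individual bowel segment sMaRIA scores will be compared"; the methods named for this are a rank test and a rank correlation. That sentence compares examinations, not readers. Narrowing, stricturing, penetrating and perianal disease are analysed as detected or not detected.

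**The concern.** Severity is an ordered item; the primary outcome itself groups its upper levels. Fleiss' kappa treats categories as unordered, so two readers who differ by one grade count as fully discordant, exactly like two readers at opposite ends of the scale. For this item the named statistic does not fit the data. The protocol is not silent here: it makes a choice, so this is more than a detail left to a later plan.

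What is at stake is the description of how reproducibly severity is graded. Section 4 foresees the abbreviated examination being used for individual follow-up and for assessing therapies, and both rest on grading. If one examination produced small grading errors and the other large ones at the same frequency, Fleiss' kappa on the grades could come out about the same for both.

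**Working it through.** The protocol states no kappa target, precision or expected agreement, so there is no figure of its own to reproduce. The calculation below is an illustration on assumed inputs.

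**Inputs.** From the protocol: Fleiss' kappa for documented features (section 9), severity among the documented items (sections 4 and 8), and about 100 participants at each of 3 sites, so about 300 (section 6). Assumed: the number of grades, their frequencies, the number of readers and the error rates.

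**Formula.** κ = (Po − Pe)/(1 − Pe), where Po is the mean weight over pairs of readers within an examination and Pe is the mean weight expected from the pooled grade frequencies. For grades i and j out of K, the weight is 1 if i = j and 0 otherwise (Fleiss), 1 − |i−j|/(K−1) (linear), or 1 − (i−j)²/(K−1)² (quadratic).

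**Illustration A.** 4 grades with true frequencies 35/25/25/15%, 4 readers, each read wrong with probability 0.20. The expected values below do not depend on the number of readers, because all pairs of readers are alike.

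- One-grade errors only. End grades move to their single neighbour; interior grades move up or down with probability 0.10 each. Two reads of an end grade match with probability 0.8² + 0.2² = 0.68, and of an interior grade with 0.8² + 2 × 0.1² = 0.66. Half the examinations are of each kind, so Po = 0.67. The pooled frequencies are 0.305, 0.295, 0.255 and 0.145, so Pe = 0.2661. Fleiss κ = 0.4039/0.7339 = 0.550.
- Errors to any other grade, equally likely. Po = 0.8² + 3 × (0.2/3)² = 0.6533. The pooled frequencies are 0.3233, 0.25, 0.25 and 0.1767, so Pe = 0.2608. Fleiss κ = 0.3925/0.7392 = 0.531.

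| Coefficient | One-grade errors: Po, Pe, κ | Any-grade errors: Po, Pe, κ | Difference in κ |
|---|---|---|---|
| Fleiss | 0.6700, 0.2661, 0.550 | 0.6533, 0.2608, 0.531 | 0.02 |
| Linear-weighted | 0.8867, 0.6160, 0.705 | 0.8074, 0.5941, 0.526 | 0.18 |
| Quadratic-weighted | 0.9600, 0.7595, 0.834 | 0.8716, 0.7330, 0.519 | 0.31 |
| Fleiss, upper two v. lower two grades | 0.9100, 0.5200, 0.813 | 0.7689, 0.5108, 0.528 | 0.28 |

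**Illustration B.** 4 equally frequent grades, 3 readers, 300 examinations, one discordant reader in a fraction f of them. One discordant reader makes two of the three pairs discordant, so Po = 1 − (2/3) × f × (1 − w), with w the weight for that disagreement. Pe is 0.25 for Fleiss and 0.7222 for quadratic weights.

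- f = 0.20, Fleiss (w = 0 for any disagreement): Po = 0.8667, κ = 0.6167/0.75 = 0.822, whether readers differ by one grade or by two.
- f = 0.20, quadratic: one grade apart (w = 8/9), Po = 0.9852, κ = 0.947; two grades apart (w = 5/9), Po = 0.9407, κ = 0.787.
- f = 0.40: Fleiss 0.644 in both cases; quadratic 0.893 against 0.573.

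**Binary items.** With K = 2 the three weightings are the same, so weighting changes nothing for the primary outcome or the present/absent features. In a simulated binary feature all three coefficients were 0.7015.

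**The case against.** The strongest reply is that the protocol names no analysis of agreement on the full severity scale. The one severity analysis it spells out is the binary moderate-severe outcome, for which Fleiss' kappa is correct. In Illustration A, Fleiss' kappa on grades cut in two (assumed upper two against lower two) is 0.81 for one-grade errors and 0.53 for any-grade errors, so it separates the two situations nearly as well as the quadratic-weighted measure. This stands as a limit: a reader who sees the binary kappa beside the full-scale kappa would not be badly misled. It does not remove the point. Severity is a documented item, the kappa sentence makes no exception for it, and a binary kappa registers only disagreements that cross the cut.

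Three stronger readings are tempting, and the documents do not support them.

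- *That kappa is fixed for every feature, sMaRIA included.* The sentence does not say so and does not name the score, which has its own sentence and methods. If kappa is not meant for sMaRIA, no inter-reader statistic is named for it here, and that can properly be left to the analysis plan.
- *That reader agreement will be misreported.* Fleiss' kappa is a valid measure of chance-corrected exact agreement. It answers a stricter question, and can lie below a weighted coefficient (0.822 against 0.947 in Illustration B) or above it (0.822 against 0.787).
- *That the two examinations will wrongly appear equally reliable, or that non-inferiority is at risk.* The protocol does not say that agreement will be compared between examinations, and the planned estimates of diagnostic performance do not use kappa.

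It is also fair to say that weights are themselves a choice: for one-grade errors, linear weights give 0.70 and quadratic weights 0.83. That is a reason to fix them in advance, not a reason to ignore the ordering.

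**Conclusion.** The point holds in a narrow form. For severity grades, the one inter-reader statistic named records exact agreement and is nearly or wholly blind to the size of a disagreement. Under the assumed inputs it moves by 0.02 (Illustration A) or not at all (Illustration B), where quadratic-weighted kappa moves by 0.31, and by 0.16 to 0.32. The sizes rest on assumed grades, frequencies and error rates; the insensitivity to distance does not, because it follows from the definition of the coefficient. The choice is sound for the binary primary outcome and the present/absent features. Inter-reader agreement is a secondary analysis, so this is a desirable improvement, not a necessary correction.

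**What to change.** Amend the kappa sentence in section 9 as follows.

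- Keep Fleiss' kappa for the binary primary outcome and the present/absent features.
- For severity grades, use a multi-rater weighted kappa. State the weights (linear or quadratic) before the reads are analysed.
- Report agreement separately for the standard and the abbreviated examination.
- If inter-reader agreement on sMaRIA is to be reported, use an intraclass correlation or a weighted coefficient, not a nominal kappa.

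The cost is a sentence of text and a few lines of code on the same reads; no new data are needed. The one drawback is that the weights are a judgement, and the result depends on them, so they must be prespecified.

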Patients will be recruited, enrolled, and imaged over a 36-month period. Data analysis will begin approximately month 30 and will require approximately 12 months to complete.

6. SELECTION & RECRUITMENT OF PARTICIPANTS:

Study sites (CCHMC, Mayo Clinic, and NYU Langone Health) will identify and recruit children and/or adults with known CD that are undergoing clinical MRE examinations for staging / restaging of intestinal inflammation, evaluation of known or suspected luminal narrowing / stricturing disease, and/or evaluation of known or suspected internal penetrating disease. CCHMC will recruit predominantly pediatric CD patients, while Mayo Clinic and NYU Langone Health will recruit

predominantly adult CD patients. Approximately one hundred participants will be enrolled and imaged at each site. Participants need to be English speaking in order to follow breath-hold commands and to complete the preference and “trade-off” surveys.

Inclusion Criteria:

Subjects will be recruited for our study using the following inclusion criteria:

- Established Crohn's disease diagnosis in patients 10 years of age and older
- Undergoing clinical MRE examinations for any reason(s) below:
 - Staging / restaging / follow-up of intestinal inflammation
 - Evaluation of known or suspected luminal narrowing / stricturing disease
 - Evaluation of known or suspected internal penetrating disease

Exclusion Criteria:

- Undergoing initial imaging for suspected CD where the diagnosis of CD has yet to be definitively established
- New CD diagnosis, undergoing baseline imaging
- Isolated colonic disease
- Known or suspected pregnancy
- Contraindication to MRI (e.g., due to certain implanted medical devices)
- Ileostomy or prior ileal resection
- Less than 10 years of age
- Unable or unwilling to follow imaging procedures
- Non-English speaking

7. PROCESS OF OBTAINING CONSENT:

Only outpatient CD patients receiving clinically indicated imaging will be recruited for this study. Participants will be screened in advance of enrollment by study personnel to determine baseline eligibility for participation. Each subject will be informed that participation in the study is completely voluntary and that he/she may withdraw from the study at any time and that withdrawal of consent will not affect his/her subsequent medical treatment or relationship with the treating physician.

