The survey will be administered on a tablet/ipad that will be supplied by a study team member. The survey will present hypothetical scenarios describing an MRE strategy. Participants will be asked to make a choice between two separate MRE imaging strategies with defined characteristics (see figure immediately below as an example). Characteristics will relate to multiple domains, including IV contrast, oral contrast, side effects such as nausea and vomiting, cost, exam time, and exam diagnostic performance. The survey will describe the attributes and walk respondents through a practice question to introduce the concept of discrete choice tasks.

If you had to choose an exam for follow-up, which exam would you prefer?		
	Option A	Option B
Accuracy	90%	80%
Exam time (minutes)	45	10
Out-of-pocket cost	\$500	\$400
IV contrast required	Yes	No
Please select one		
If you had to choose an exam for follow-up, which exam would you prefer?		
	Standard MRE	
	Abbreviated MRE	
	I don't know	

Study Chronology:

Procedure:
Telephone NPO Consent*
Informed Consent
Medical History
Clinical MR
Abbreviated Research MRE**
Patient Experience and Preference Survey (Discrete Choice Experiment)***

*Using the phone script, verbal consent will be obtained prior to the research MRI study to confirm participants will not eat or drink for 4 hours prior to the research MRE.

**Research MRE may occur ± 10 days from Clinical MRE.

*** Once the research MRE and the clinical MRE are completed, participants and a parent of a participant age 10-17 will be asked to complete a questionnaire. This may require a second research encounter depending upon whether the research MRE or clinical MRE is performed first.

The participants must be nil per os (NPO) 4 hours prior to both the clinical and research MRE exams. If a participant is not NPO 4 hours prior to their MRE exams and is able to reschedule within window (if applicable) the participants visit(s) will be rescheduled.

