We will estimate preferences for imaging using a mixed logit model (i.e., a random coefficient logit model), a statistical model designed to analyze discrete choices. Variation in preferences related to health and demographic characteristics will be captured through specification of covariates in the model. The coefficients of each attribute in the mixed logit model represent estimates of the probability of choosing an imaging strategy as a function of the levels of the attributes. Results from the main effects model will be used to estimate the marginal willingness to accept an imaging strategy for each level of an attribute by looking at the ratios of the coefficients between an attribute level. Statistical significance from 0 for coefficients t will be assessed at p-value <0.05.

The survey will include an attention check to determine whether respondents will choose the correct alternative when one choice is clearly the same or better on all attribute levels. We will run sub-analyses that eliminate responses that failed the attention check twice.

No identifiable information will be provided via the Sawtooth survey. Therefore, risks of respondent's privacy being breached online will be minimal.

10. FACILITIES and PERFORMANCE SITES:

The proposed study will be performed at three sites – CCHMC, Mayo Clinic, and New York University Langone Health. CCHMC will be the lead site and serve as the Institutional Review Board of record for all participating sites. Clinical imaging will be performed using MRI scanners in approved clinical locations, while research imaging will be performed using dedicated research scanners that are FDA-cleared for clinical use and that are operated within appropriate safety limits.

11. POTENTIAL BENEFITS:

There are no direct study-related benefits. However, participants could benefit from our abbreviated research MRE protocol in the future, should it be determined to be non-inferior to conventional, standard of care MRE. The abbreviated MRE could be better tolerated, allow more frequent imaging, have shorter examination times, and have lower healthcare costs.

12. POTENTIAL RISKS, DISCOMFORTS, INCONVENIENCES AND PRECAUTIONS:

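### The survey analysis tests continuous outcomes across groups only with t-tests, but its first example, income level, has three groups

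*Protocol*

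**What the plan says.** The Survey Analysis part of Section 9 summarizes continuous outcomes by means and standard deviations, compares them across groups, and names one test for doing so. The examples of groups and the test stand together: "e.g. low versus middle versus high income levels, parent education level, proportion using a CGM) and test for statistical differences between groups using t-tests".

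Three other statements bear on the point:

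- For categorical outcomes, the next sentence reads: "We will summarize categorical outcome measures using frequencies and proportions and test for statistical differences between groups using chi-square tests".
- For the discrete choice data, a mixed logit model is planned, and "Variation in preferences related to health and demographic characteristics will be captured through specification of covariates in the model".
- The only significance level in the survey analysis is for the coefficients of that model: "Statistical significance from 0 for coefficients t will be assessed at p-value <0.05".

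On numbers, Section 6 says "Approximately one hundred participants will be enrolled and imaged at each site", and there are three sites. Under Study Chronology in Section 8, "participants and a parent of a participant age 10-17 will be asked to complete a questionnaire".

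**The concern.** The test and its example do not fit each other. A two-sample t-test compares two means, whereas low, middle and high income make three groups. Taken literally, the text cannot answer whether a continuous outcome differs by income level. The analyst would have to improvise by testing one pair, merging levels, or testing every pair. The first two leave part of the stated comparison untested. The third raises the chance of a false difference unless something controls it, and the protocol states no control.

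The same problem would arise for parent education if it is recorded in more than two categories, which the protocol does not say.

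The third example in the parenthesis, on CGM use, is a clerical matter. The abbreviation is not defined, the item appears nowhere else in the protocol, and a proportion is not a grouping factor as worded.

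**Working it through.** **Is the mismatch cured elsewhere in the protocol?**

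- The chi-square tests can handle three groups, but they are assigned to categorical outcomes.
- The covariates can carry income or education, but they enter the model of the discrete choices, not the analysis of continuous outcome measures.
- No ANOVA, rank test, linear regression, global test, pairwise rule or multiplicity adjustment is named for these comparisons.

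So it is not cured. The protocol gives no error rate or power for this comparison, so there is no stated figure to reproduce. The rest of the check sizes the consequence of one possible procedure.

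**Inputs**

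- Groups: 3 (the income example in Section 9), so 3 × 2 / 2 = 3 pairs.
- Respondents: about 100 at each of 3 sites, so about 300 (Section 6).
- Level: two-sided 0.05 per test. This is an assumption, because the protocol gives 0.05 only for the mixed logit coefficients. Results for 0.01 and 0.10 are shown as the range.
- Split across income levels: not given, so several are assumed.

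**Simple bounds at 0.05.** If the three tests were independent, the chance of at least one false difference would be 1 − 0.95³ = 14.3%. The upper bound is 3 × 0.05 = 15%. The real tests share groups and so are correlated, which puts the true figure lower.

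**Exact value, equal groups of 100, pooled variance.** At least one of the three pairs is significant when the studentized range exceeds √2 times the t critical value, with 3 groups and 300 − 3 = 297 degrees of freedom.

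| Level per test | t critical value | √2 × t | P(at least one false difference) |
|---|---|---|---|
| 0.01 | 2.592 | 3.666 | 2.7% |
| 0.05 | 1.968 | 2.783 | 12.2% |
| 0.10 | 1.650 | 2.333 | 22.6% |

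**Simulation at 0.05.** Normal outcomes with SD 1, no true difference, 20,000 replicates:

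| Group sizes | Any of 3 unadjusted pairs | One-way ANOVA | Pairs only after a significant ANOVA |
|---|---|---|---|
| 100 / 100 / 100 | 12.2% | 5.4% | 5.4% |
| 60 / 150 / 90 | 11.8% | 4.9% | 4.9% |
| 30 / 210 / 60 | 12.0% | 4.9% | 4.8% |

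The simulation standard error is about √(0.12 × 0.88 / 20,000) = 0.2 percentage points for the pairwise column and √(0.05 × 0.95 / 20,000) = 0.15 points for the other two. The split therefore makes little difference.

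**Does the proposed rule hold when one group really differs?** With 100 per group and the third group shifted by 0.3, 0.6 or 1.0 SD, a false difference between the two equal groups, declared only after a significant ANOVA, occurred in 4.7%, 5.1% and 5.1% of replicates. With three groups, the rule keeps the error near 5%.

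**The case against.** The strongest reply is that the text has a workable reading. It speaks of t-tests in the plural and does not say that income will be tested as a whole. Pairwise t-tests fit those words, and each is valid at its own level. What remains is then multiplicity in a secondary survey comparison, which is often left to a statistical analysis plan, and the protocol claims no familywise control for the survey. The 12% needs four conditions together: all pairs tested, a level of 0.05, no adjustment, and no true difference.

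Two further points concern reach. The protocol names no continuous survey outcome, and the survey items it displays are categorical, so few analyses may use these t-tests. The example list also looks loosely tailored to this study, so correcting the examples might remove much of the mismatch.

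Much of this stands as a limit on weight. The 12% is a conditional illustration, and it sets a rate over three tests against a level for one. The number of affected outcomes is unknown. Adding about 100 parents as further respondents gives almost the same result (11.9% to 12.3% for two splits of 400). That scenario treats parents as independent of their children, which is doubtful, and nothing here rests on it.

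The reply does not remove the point. The pairwise reading is the one that produces the inflation. Nor is this detail merely deferred to another document, because the protocol itself names a test and gives an example that the test does not fit. Editing the examples would help, but parent education may also have more than two levels.

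**Conclusion.** The sentence is wrong as written: the only test named for continuous outcomes does not fit the first factor given as an example, and nothing else in the protocol repairs this. That conclusion needs no assumptions.

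The size of the consequence does need them. If all three income pairs are tested unadjusted and no true difference exists, the chance of a false finding per outcome is about 12% at an assumed level of 0.05, against about 5% with a global test. At 0.01 and 0.10 it is likewise more than double the level used.

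Severity is minor. The affected comparisons are secondary, and the conclusions on diagnostic performance, the categorical survey results and the modelled preferences do not depend on them.

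**What to change.** Reword the sentence in the Survey Analysis part of Section 9 along these lines:

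- For grouping factors with two levels, keep the t-test.
- For factors with three or more levels, use a one-way ANOVA, a Kruskal-Wallis test or a linear regression with a global test of the factor.
- Make pairwise comparisons only after a significant global test, with a multiplicity adjustment if there are more than three levels.
- State the significance level for these comparisons.
- Delete the item on CGM use, or define it as a grouping factor and say where it is collected.

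The cost is wording only. No new data, visits or participants are needed.
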